4.2 Exclusion Criteria (Step 1)

4.2.1 Positive for the presence of hepatitis B virus (HBV) surface antigen (HBsAg).

4.2.2 For cirrhotic participants, CTP score >6 corresponding to Class B or C (Please refer to the A5360 PSWP for the website link to calculate the CTP score).

4.2.3 Breastfeeding or pregnancy.

4.2.4 Known allergy/sensitivity or any hypersensitivity to components of study drug(s) or their formulation.

4.2.5 Active drug or alcohol use or dependence and other conditions that, in the opinion of the site investigator, would interfere with adherence to study requirements.

4.2.6 Acute or serious illness requiring systemic treatment and/or hospitalization within 35 days prior to study entry.

4.2.7 In HIV positive participants, presence of active or acute AIDS-defining opportunistic infections within 35 days prior to study entry.

NOTE: AIDS-defining opportunistic infections as defined by the CDC found in the following document: <http://www.cdc.gov/mmwr/preview/mmwrhtml/00018871.htm>

4.2.8 Any history of hepatic decompensation including ascites, spontaneous bacterial peritonitis, hepatic encephalopathy, hepatorenal syndrome, and/or bleeding esophageal varices prior to study entry.

4.2.9 Use of prohibited medications within the past 14 days prior to study entry (please refer to the A5360 PSWP for the list of prohibited medications).

NOTE: ART regimens must not contain prohibited medications (please refer to the A5360 PSWP for the list of prohibited medications).

4.3 Inclusion Criteria (Step 2)

4.3.1 Completion of SVR evaluation visit in Step 1.

4.4 Exclusion Criteria (Step 2)

There are no exclusion criteria for Step 2.

4.5 Study Enrollment Procedures

4.5.1 Prior to implementation of this protocol, and any subsequent full-version amendments, each site must have the protocol and the protocol consent form(s) approved, as appropriate, by their local institutional review board (IRB)/ethics committee (EC) and any other applicable regulatory entity (RE). Upon receiving final approval, sites will submit all required protocol registration documents to the DAIDS Protocol Registration Office (DAIDS PRO) at the Regulatory Support Center (RSC). The DAIDS PRO will review the submitted protocol registration packet to ensure that all of the required documents have been received.

Site-specific informed consent forms (ICFs) WILL be reviewed and approved by the DAIDS PRO, and sites will receive an Initial Registration Notification from the DAIDS PRO that indicates successful completion of the protocol registration process. A copy of the Initial Registration Notification should be retained in the site's regulatory files.

Upon receiving final IRB/EC and any other applicable RE approval(s) for the amendment, sites should implement the amendment immediately. Sites are required to submit an amendment registration packet to the DAIDS PRO at the RSC. Site-specific ICF(s) WILL be reviewed and approved by the DAIDS PRO, and sites will receive an Amendment Registration Notification from the DAIDS PRO that approves the site-specific ICFs and indicates successful completion of the amendment protocol registration process. A copy of the final Amendment Registration Notification issued by the DAIDS PRO should be retained in the site's regulatory files.

For additional information on the protocol registration process and specific documents required for initial and amendment registrations, refer to the current version of the DAIDS Protocol Registration Manual.

Once a candidate for study entry has been identified, details will be carefully discussed with the participant. The participant will be asked to read and sign the approved protocol consent form.

For participants from whom a signed informed consent has been obtained, an ACTG Screening Checklist must be entered through the Data Management Center (DMC) Participant Enrollment System.

4.5.2 Protocol Activation

Prior to enrollment, sites must complete the Protocol Activation Checklist found on the ACTG Member website. This checklist must be approved prior to any screening of participants for enrollment.

4.5.3 Participant Registration

For participants from whom informed consent has been obtained, but who are deemed ineligible or who do not enroll into the initial protocol step, an ACTG Screening Failure Results form must be keyed into the database.

Participants who meet the enrollment criteria will be registered to the study according to standard ACTG DMC procedures.

4.6 Co-enrollment Guidelines

US sites are encouraged to co-enroll participants in A5128, "Plan for Obtaining Informed Consent to Use Stored Human Biological Materials (HBM) for Currently Unspecified Analyses." Co-enrollment in A5128 does not require permission from the A5360 protocol chairs.

Non-US sites are encouraged to co-enroll participants in A5243, "Plan for Obtaining Human Biological Samples at Non-U.S. Clinical Research Sites for Currently Unspecified Genetic Analyses." Co-enrollment in A5243 does not require permission from the A5360 protocol chairs.

For specific questions and approval for co-enrollment in other studies, sites should first check the PSWP or contact the protocol team via email as described in the Study Management section.

If there are concerns about exceeding volume limits for blood draws, please note that A5128 and A5243 allow participants to consent to the study without allowing a blood sample to be collected. In these cases, if a future study wants to evaluate a participant's DNA sometime later, sites would be able to access a stored aliquot from the initial study (if there are any available). It is also possible for a participant to enroll into A5128 or A5243 and postpone the required blood draw until a later time. For more input, contact the A5128 or A5243 teams.

5.0 STUDY TREATMENT

Study treatment is defined as the once-daily oral FDC sofosbuvir/velpatasvir (SOF/VEL [Tradename: Epclusa]) containing 400 mg of SOF and 100mg of VEL. If a participant is co-infected with HIV, HIV medications will NOT be provided as part of this study.

5.1 Regimens, Administration, and Duration

5.1.1 Regimens

Participants will receive FDC SOF/VEL (400mg/100mg) orally once daily with or without food.

5.1.2 Administration and Duration

Participants will take SOF/VEL orally once daily with or without food and will receive treatment for a duration of 12 weeks. Study staff will observe the first dose being taken by the participant upon completion of all entry evaluations. Participants should be instructed to open and finish one bottle of study product at a time. When the participant takes the last pill of SOF/VEL from each bottle, he/she will be instructed to contact the site to report the completion of the bottle. Participants will, therefore, contact a site a maximum of three times to indicate completion of a bottle. See A5360 MOPS for additional information on reporting of treatment stop date.

In the scenario of lost study medication, the participant will be asked to contact the study site as soon as possible. If the participant has been off study medication less than 2 weeks (≤ 14 days), he/she will be eligible for a one-time replacement of study medication to complete the 12 week course. Participants who report a subsequent loss of study medication will not be eligible for replacement and will enter the follow-up phase (week 24 visit). If the participant has not taken study medication for more than 2 weeks (≥ 15 days), study medication will not be replaced and the participant will enter the follow-up phase (week 24 visit).

5.2 Study Product Formulation and Preparation

5.2.1 Sofosbuvir/Velpatasvir manufactured by Gilead Sciences, Inc., will be supplied as 400/100 mg film-coated tablets for oral administration. Store below 30°C (86°F). Dispense only in original container.

5.3 Pharmacy: Product Supply, Distribution, and Accountability

5.3.1 Study Product Acquisition/Distribution

The FDC of SOF/VEL will be provided by Gilead Sciences, Inc. and will be available through the NIAID Clinical Research Products Management Center (CRPMC). The site pharmacist should obtain the study product(s) for this protocol by following the instructions in the manual *Pharmacy Guidelines and Instructions for DAIDS Clinical Trials Networks*.

Any study product not provided by the study must comply with the NIAID (DAIDS) policy that outlines the process for authorizing the use of study products not marketed in the US in NIAID (DAIDS)-supported and/or – sponsored clinical trials. This policy is available on the NIAID (DAIDS) website at: <https://www.niaid.nih.gov/sites/default/files/NonFDAapprovedProducts.pdf>.

5.3.2 Study Product Accountability

The site pharmacist is required to maintain complete records of all study products received from the NIAID CRPMC and subsequently dispensed. At US CRSs, all unused study products must be returned to the NIAID CRPMC (or as otherwise directed by the sponsor) after the study is completed or terminated. The procedures to be followed are provided in the manual *Pharmacy Guidelines and Instructions for DAIDS Clinical Trials Networks*. At non-US CRSs, the site pharmacist must follow the instructions in the *Pharmacy Guidelines and Instructions for DAIDS Clinical Trials Networks* for the destruction of unused study products.

5.4 Concomitant Medications

Whenever a concomitant medication or study agent is initiated or a dose changed, investigators must review the concomitant medication's and study agent's most recent package insert, Investigator's Brochure, or updated information from DAIDS to obtain the most current information on drug interactions, contraindications, and precautions.

Additional drug information may be found on the ACTG Precautionary and Prohibited Medications Database located at: http://tprc.pharm.buffalo.edu/home/di_search/.

5.4.1 Prohibited Medications

Please refer to the A5360 PSWP for the list of prohibited medications.

5.4.2 Precautionary Medications

Please refer to the A5360 PSWP for the list of precautionary medications.

6.0 CLINICAL AND LABORATORY EVALUATIONS

6.1 Schedule of Evaluations

6.1-1: Schedule of Evaluations: Step 1- Visits up Until SVR Evaluation

Evaluation	Screening	Entry/Week 0	Weeks			SVR Evaluation Visit (if week 24 visit is missed; can occur up to week 72)	Unplanned Study Visits (see section 6.2.6)
			4	22	24		
			Window \pm 7 days		Window -14/+28 days		
Documentation of Active HCV Infection	X						
Documentation of HIV-1 Status	X						
Calculated FIB-4 Score	X				X	X	As needed.
MELD Score		X					
Documentation of Cirrhosis Status	X				X	X	As needed.
Calculated CTP Score (if cirrhotic by FIB-4)	X				X	X	
Liver Elastography (see section 6.3.7)		X			X	X	
Medical History	X	X					
Medication History	X	X					
Clinical Assessments	X	X			X	X	As needed.
Hematology	X	X			X	X	
Liver Function Tests	X	X			X	X	
Blood Chemistries	X	X			X	X	As needed.

Evaluation	Screening	Entry/Week 0	Weeks			SVR Evaluation Visit (if week 24 visit is missed; can occur up to week 72)	Unplanned Study Visits (see section 6.2.6)
			4	22	24		
			Window \pm 7 days		Window -14/+28 days		
Calculated Creatinine Clearance	X						
INR	X				X	X	As needed.
Pregnancy Testing	X	X			If pregnancy is suspected.		
HBV Panel	X						
CD4+ (if HIV+)	X				X	X	
Plasma HIV-1 RNA (if HIV+)	X				X	X	
Plasma HCV RNA	X				X	X	
Stored Plasma/PBMC/Serum		X			X	X	As needed. (Plasma sample will be stored if blood sample obtained.)
Adherence Assessment			X (via remote contact)		X	X	
Health Outcomes Questionnaire		X			X	X	X
Health Care Utilization Questionnaire		X			X	X	X
Substance Use Questionnaire		X			X	X	

Evaluation	Screening	Entry/Week 0	Weeks			SVR Evaluation Visit (if week 24 visit is missed; can occur up to week 72)	Unplanned Study Visits (see section 6.2.6)
			4	22	24		
			Window \pm 7 days		Window -14/+28 days		
HCV Therapy Dispensed/First Dose Observed		X					
Adherence Education and Counseling		X					
Pregnancy Prevention Counseling	X	X					
Cirrhosis Counseling		X			X	X	
HCV Risk-reduction Counseling		X			X	X	
Locator Information		X	Update information, if needed.				
Remote Contact with Participants Outside of Planned Clinic Visits			X	X (see note in section 6.2.4)			

6.1-2: Schedule of Evaluations: Step 2- Visits Post SVR Evaluation

Evaluation	Weeks			
	42	48	68	72
	Window +28 days			
Calculated FIB-4 Score		X		X
MELD Score		X		X
Calculated CTP Score (if cirrhotic by FIB-4)		X		X
Liver Elastography (see section 6.3.7)		X		X
Clinical Assessments		X		X
Hematology		X		X
Liver Function Tests		X		X
Blood Chemistries		X		X
Calculated Creatinine Clearance		X		X
INR		X		X
Plasma HCV RNA (if SVR responder)		X		X
Stored Plasma/PBMC/Serum		X		X
Health Outcomes Questionnaire		X		X
Health Care Utilization Questionnaire		X		X
Substance Use Questionnaire		X		X
Cirrhosis Counseling		X		X
HCV Risk-reduction Counseling		X		X
Remote Contact with Participants Outside of Planned Clinic Visits	X		X	

6.2 Timing of Evaluations

6.2.1 Screening Evaluations

Screening evaluations must occur prior to the participant starting any study medications, treatments, or interventions.

Screening evaluations to determine eligibility must be completed within 35 days prior to study entry unless otherwise specified in section 4.0.

In addition to data being collected on participants who enroll into the study, demographic, clinical, and laboratory data on persons who do not enroll will be captured in an eCRF and entered into the ACTG database.

6.2.2 Step 1 Entry Evaluations

Step 1 entry evaluations must occur at least 24 hours after screening evaluations, unless otherwise specified.

Participants are expected to begin treatment with SOF/VEL within 24 hours after registration and upon completion of entry evaluations. The first dose of SOF/VEL will be provided to the participant and observed by study staff.

6.2.3 Step 2 Registration Evaluations

Participants who meet criteria in section 4.3 will register to Step 2 on the same day of the last visit on Step 1 and be followed per the SOE.

6.2.4 Post-Entry Evaluations

Given the design of the MINMON strategy, there will be no on-treatment or EOT evaluations. See section 6.3.22 for post-entry site contact with participants via remote mechanism.

Post-Treatment Evaluations

Step 1: Following treatment completion at week 12, participants will undergo evaluations as outlined in the SOE 6.1-1.

NOTE: If the participant comes in for the week 24 visit during the -14 days window (i.e., week 22), then the week 22 remote call is not needed.

Week 24/SVR Evaluation Visit

The week 24 visit (visit window: week 22-28) is ideally the visit where SVR should be assessed for all participants, and subsequently they will be registered to Step 2. However, if a participant misses the visit window (>week 28), the week 24 visit will be considered a missed visit and he/she will need to be scheduled for an SVR visit prior to being registered to Step 2 of the study. The SVR visit can

take place at any time point after week 28 and up to week 72 and is mandatory for the participant to be registered to Step 2.

NOTE: Participants will be reminded of the week 24/SVR visit during the remote contact (at weeks 4 and 22), and participants only need to complete either the week 24 OR the SVR evaluation visit; they will not be required to complete both. If a participant completes week 24, his/her next visit will be at week 48 on Step 2. If a participant misses the week 24 visit and returns to the clinic for the SVR visit either at week 48 or 72, then only the SVR evaluations will be performed at that visit time point. Evaluations for weeks 48 or 72 will be performed at the next scheduled study visit. However, if a participant completes their SVR visit at week 72, this visit will be the participants' last study visit and they will not enter Step 2.

Step 2 Registration

Following completion of the SVR evaluation on Step 1 (Week 24 OR SVR visit), participants will be registered to Step 2 on that same day. Participants will undergo evaluations as outlined in the SOE 6.1-2, within the ±28-days visit window, as appropriate for the visit.

NOTE: Participants who register into Step 2 within the week 48 visit window will complete the week 48 and 72 visits. If a participant registers into Step 2 after the week 48 visit window, site staff should have the participant return to the clinic to complete week 72 (final study visit).

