10.0 STATISTICAL CONSIDERATIONS

10.1 General Design Issues

This is a single-arm study of 400 participants, to evaluate the feasibility, safety, and efficacy of a MINMON strategy of delivering interferon and RBV-free, pan-genotypic DAA therapy to qualifying persons with active HCV. The outcomes of this study may be used to inform the feasibility and utility of a future randomized controlled trial including a study arm with the MINMON strategy. Because this study includes only one arm, there is no blinding of any study intervention component.

The primary completion date (PCD) for each participant will be timed to be the date when the SVR evaluation takes place. As defined below, SVR evaluation will take place at least 22 weeks following study entry, but may take place any time up to 76 weeks following study entry (i.e., the final study visit evaluation).

Following SVR evaluation, participants will enter Step 2 for post-SVR evaluation follow-up for secondary and exploratory objectives.

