2.1 Purpose and Scope

This Primary Statistical Analysis Plan (SAP) describes the primary and secondary outcome measures and additional outcome measures of the A5360 study that will be included in the primary manuscript, and which address, at a minimum, the major primary and secondary objectives of the study. The Primary SAP outlines the general statistical approaches that will be used in the analysis of the study. It has been developed to facilitate discussion of the statistical analysis components among the study team, and to provide agreement between the study team and statisticians regarding the statistical analyses to be performed and presented in the primary analysis report. It also describes the results for the primary and secondary outcome measures that will be posted on ClinicalTrials.gov.

Detailed outlines of tables, figures, and coding descriptions that will be included in the Primary Analysis Report are included in a separate document called the Primary Analysis Implementation Plan (AIP).

Analyses for the Primary Analysis Report will be triggered by the study's primary completion date (PCD) which is defined as the date when the Sustained Virologic Response (SVR) evaluation visit has occurred for all participants enrolled. The SVR evaluation visit is the first clinic visit occurring more than 22 weeks post study entry (and up to 76 weeks post entry), where samples for HCV RNA were collected). These analyses will be finalized after all queries have been resolved.

Analyses not included in this document (i.e. those planned for manuscripts subsequent to the primary one), will be outlined in a separate, Secondary Statistical Analysis Plan, and parallel Secondary AIP.

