4.1 Primary Outcome Measures

4.1.1 Primary Efficacy Outcome Measure

Measure Title: *Percentage of Participants with Sustained Virologic Response 12 (SVR12)*

Measure Description: *SVR12 was defined as plasma HCV RNA less than the lower limit of quantification (LLOQ) from the earliest sample drawn at least 22 weeks following study treatment initiation (i.e. at a visit scheduled at least 10 weeks after scheduled end of study treatment). Participants without any HCV RNA result at least 22 weeks after treatment initiation will be considered as having HCV RNA greater than the LLOQ.*

A two-sided 95%, confidence interval was calculated for this percentage using the Wilson (score) method.

Time Frame: *At least 22 weeks and up to 76 weeks from treatment initiation.*

Population Description: *Participants who enrolled and received first dose of study medication.*

Associated study objective: *“To estimate SVR (defined as HCV RNA < lower limit of quantification [LLOQ] at least 10 weeks after the end of treatment [EOT] [which is at least 22 weeks from the study entry visit date]).”*

Details: Due to the definition of SVR outcome measure, missing HCV RNA results will lower the overall percentage of participants with SVR. Therefore, various reasons for non-SVR (e.g., discontinued treatment early due to various reasons including intolerance, observed HCV RNA \geq LLOQ, missing evaluation for SVR (and reasons as known), and the number of participants meeting each reason for non-SVR, will be presented in order to interpret the overall SVR sample estimate.

For interim analyses: Interim analysis is planned when SVR outcomes are available for approximately 100 participants. At interim reviews, SVR will be calculated only among those with potential to contribute to SVR (by having at least 22 weeks elapsed since study entry). Imputation of missing SVR evaluation as non-SVR response will only occur for participants for whom more than 76 weeks since study enrollment has elapsed. In other words, early study discontinuations prior to week 22 will not be counted in SVR estimation at interim review, as these could bias the estimation of SVR towards futility. Instead, these early study discontinuations prior to week 22 (before available for SVR evaluation), and others missing SVR evaluation, will contribute to the interim monitoring

trigger. For more details, refer to Overview of Formal Interim Monitoring of section 3.5 above.

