5.1.2 Clinic Study Visit Windows

MINMON intervention EPOCH [Step 1]: The first follow-up clinic visit at study week 24, for primary outcome SVR evaluation has a window of -14 days to +28 days. If week 24 study visit is missed, this “primary SVR evaluation” visit can occur anytime up to study week 72 which is the end of study follow-up.

Post SVR, post MINMON, or follow-up EPOCH [Step 2]: Two clinic visits are scheduled post SVR at week 48 and 72. The ranges of week 48 clinic visits were examined and the observed range is used for visit window; weeks 48 has a window of -28/+60 days. Week 72 has a window of \pm 28 days.

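### The site instructions close a late first SVR visit at week 72, four weeks before the outcome definition stops accepting the sample (minor)

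*Protocol*

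**What the plan says.** **Places that stop at week 72**

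- Protocol 6.2.4, on the SVR visit for a participant who missed the week 24 window: "take place at any time point after week 28 and up to week 72 and is mandatory for the participant to be registered to Step" (meaning Step 2).
- Protocol Table 6.1-1 (Step 1 schedule), column heading: "SVR Evaluation Visit (if week 24 visit is missed; can occur up to week 72". Weeks 4, 22 and 24 have windows in this table. The late SVR column has none. Clarification Memo #2 reissued the table with the same heading.
- SAP 5.1.2, Step 1 paragraph: the visit "can occur anytime up to study week 72 which is the end of study follow-up".

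**Places that run to week 76**

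- Protocol 10.1: SVR evaluation happens at 22 weeks or later, "but may take place any time up to 76 weeks following study entry". It equates that limit with the final study visit.
- SAP 4.1.1, time frame: "At least 22 weeks and up to 76 weeks from treatment initiation".
- SAP 2.1 also gives 76 weeks after entry as the upper limit.
- The interim rules (protocol 10.5.1, SAP 4.1.1 and SAP 5.1.3) impute a missing result as non-response only once more than 76 weeks have passed since enrollment.

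**Places with no upper limit**

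- Protocol 10.2.1.1 takes the earliest sample at 22 weeks or later and treats missing results as non-response.
- SAP 5.1.1 takes the earliest valid result in the SVR evaluation window. It states when that window starts but not when it ends.

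**The concern.** The primary efficacy outcome counts a participant with no HCV RNA result as a non-responder. The last day on which a site will draw the first SVR sample therefore matters: up to that day a late returner is scored on virology, and afterwards on absence. If the site's last day is four weeks earlier than the analysis's last day, the trial can lose outcomes that its own definition would accept, and each one lost counts against the strategy.

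Protocol 2.2 treats this kind of loss as important. It says that about 20% of US patients who complete treatment do not come back for SVR assessment on time. It also adds an incentive for the SVR visit, because a non-returner counts as a failure even if cured. The 20% is general background. It does not estimate how many trial participants would first return in weeks 72-76.

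**Working it through.** **1. Where week 76 comes from.** Protocol 6.2.5 and SAP 5.1.2 give the week 72 visit a window of 28 days either side: 72 + 28/7 = 76.0 weeks. This reproduces the limit in protocol 10.1, SAP 2.1 and SAP 4.1.1, so the two limits are probably a nominal visit week and the end of its window.

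**2. Whether that window reaches the participant concerned.**

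- The 28 days appear in Table 6.1-2 (Step 2 schedule), in the Step 2 Registration part of 6.2.4, in the Step 2 sentence of 6.2.5, and in the Step 2 paragraph of SAP 5.1.2.
- Step 2 entry requires a completed SVR visit (protocol 4.3.1), so a participant without an SVR sample is in Step 1.
- Under 6.2.4, a participant whose SVR visit falls at week 72 never enters Step 2.
- The COVID-19 letters and memo extend the week 72 visit by amending Table 6.1-2. The US extension also requires a completed week 24/SVR visit. They do not settle the Step 1 limit.

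No text applies the 28 days to a late first SVR visit.

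**3. What happens to a first return in weeks 72-76.**

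| Situation | Result under the documents |
|---|---|
| Sample drawn | Scored: within the SAP 4.1.1 time frame, and 10.2.1.1 has no upper limit |
| Sample not drawn because the site stops at week 72 | Missing, hence non-responder |

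**4. Benchmark cut-offs reproduced.** Inputs: n = 400, Wilson 95% interval, HIGH at 392 or more responders and LOW at 371 or fewer (protocol 10.4 and 10.6.1). With p = x/n and z = 1.96, the limits are

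[p + z²/(2n) ± z·√(p(1−p)/n + z²/(4n²))] / (1 + z²/n)

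| Responders of 400 | Lower limit | Upper limit | Benchmark |
|---|---|---|---|
| 392 | 96.10% | 98.98% | HIGH met |
| 391 | 95.78% | 98.81% | HIGH not met |
| 372 | 90.07% | 95.11% | LOW not met |
| 371 | 89.78% | 94.91% | LOW met |

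The exact binomial P(X ≥ 392) with n = 400 is 0.059, 0.151, 0.593 and 0.849 at true SVR 96.5%, 97%, 98% and 98.5%. Table 10.4-1 gives .06, .15, .59 and .85, so the plan's figures reproduce.

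**5. Size.** One lost responder is 1/400 = 0.25 percentage points. Suppose k participants are certain to be counted as failures because no sample was drawn. Then P(HIGH) = P(Binomial(400 − k, p) ≥ 392). The documents give no value for k, so the values below are assumptions.

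| True SVR | k = 0 | k = 1 | k = 2 |
|---|---|---|---|
| 98.5% | 0.85 | 0.75 | 0.61 |
| 98% | 0.59 | 0.45 | 0.32 |

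For one such participant, the chance that the HIGH result flips is about 0.85 − 0.75 = 0.10 at 98.5% and 0.59 − 0.45 = 0.14 at 98%.

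**The case against.** The strongest reply is that nothing is in conflict: week 72 is the visit, week 76 is the end of its window, and 10.1 says as much by tying 76 weeks to the final study visit. Protocol 6.2.4 foresees an SVR visit made at week 72 and makes it the last visit. Protocol 6.2.5 says that, for those who never enter Step 2, the last Step 1 visit is the final one whenever it happened. No sentence tells a site to turn anyone away. As a reading of intent this stands. It does not remove the gap in the site-facing text, because the Step 1 table gives windows to its other post-entry visits and none to this one, and SAP 5.1.2 calls week 72 the end of follow-up.

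A reader might go further and infer that a sample drawn in weeks 72-76 is a result under one section and a failure under another. The documents do not support that. SAP 5.1.2 says when a visit can occur and is not a scoring rule. SAP 4.1.1 counts the sample, and it imputes failure only where there is no HCV RNA result at 22 weeks or later. The missing end date in SAP 5.1.1 leaves room for a strict reading, but no section states one.

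A reader might also take the 20% figure as a sign that many are affected. It does not show that: it concerns timely return among US patients in general, and this trial has a week 22 contact and an incentive.

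The lower bound also differs: SAP 2.1 says "The SVR evaluation visit is the first clinic visit occurring more than 22 weeks post study entry", while protocol 10.2.1.1 and SAP 4.1.1 include week 22 itself. SAP 2.1 describes the trigger for the primary report, the outcome definitions agree with each other, and no result changes.

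**Conclusion.** The point holds as a minor one. The closing date that sites are given for a late first SVR visit is four weeks earlier than the one the outcome definition accepts, and the window that would join them is written for a step the participant has not reached. The consequence is a possible avoidable loss of primary-endpoint samples, not contradictory scoring.

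The number affected is unknown and may be zero. Each responder lost costs 0.25 points of SVR. One such loss alters a benchmark result only if the total would otherwise be exactly 392 (HIGH lost) or exactly 372 (LOW gained). The probabilities for one or two losses rest on an assumed count, and on the sites concerned reading week 72 literally and drawing no sample.

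**What to change.** - In protocol 6.2.4, the late SVR column of Table 6.1-1, and the Step 1 paragraph of SAP 5.1.2, state that a participant without an SVR sample may have the SVR visit through week 76 (week 72 + 28 days).
- In SAP 5.1.1, end the SVR evaluation window at week 76.
- As housekeeping only, change SAP 2.1 so that week 22 itself is included, as in protocol 10.2.1.1 and SAP 4.1.1.

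The cost is a few lines in a letter of amendment and in the SAP. The only practical downside is that a few SVR visits may take place up to four weeks later, still within the 76 weeks that the analysis already allows.
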